Diagnostic Ultrasound Imaging will be performed by a trained Sonographer using the Spark® Imaging System, manufactured by Ardent Sound, Inc., Mesa, AZ USA (Appendix 7-B)

Subjects will be imaged seated with their arm resting on a structure that is comfortable for the subject and sonographer.

PolySonic® or AquaSonic® Gel will be applied by the sonographer as required to maintain adequate acoustic coupling. (Appendix 7-C)

1

[figure not shown]
Images will be preserved with the following notations:

- Protocol ID
- Right vs. Left CET Tendon
- Treated vs. Untreated

Long Axis and Short Axis (if necessary) images will be stored at the Sonographer's discretion, to demonstrate and track the applicable anatomy/pathology in the peri-CET area.

Sonographer will also measure the thickness of the CET tendon in each applicable image.

Sonographer will scan the contralateral CET tendon in the same manner noting the change in the tendon (Right v. Left) and (Treated v. Untreated).

Common Extensor Tendon
Figure 4: representative long axis ultrasound images

Outcome measures

Subjects will complete subject reported outcome measures at 0, 2, 4, 8, 12, and 24 weeks and will undergo a focused physical examination and diagnostic ultrasound at 0, 2, 4, and 8 weeks. Adverse events will be recorded at each visit. Treatment tolerability will be assessed immediately after each treatment using the Visual Analog Scale for Pain (VAS) or Universal Pain Assessment Tool (Appendix 3-B). The VAS will be used for 2 different assessments: 1. Pain related to physical activity of the symptomatic arm before treatments and at follow-up visits and phone surveys. 2. Pain tolerance of the therapy treatment. Each of these assessments will be documented and evaluated separately.

Aim 1: reported outcomes

The principal aim of this study is to assess the efficacy of treatment and time course of response to treatment using validated subject reported outcome measures assessing pain, function and level of activity. Subjects will complete validated subject reported outcome questionnaires assessing pain, function and level of activity prior to initiating treatment and at

0, 2, 4, 8, 12, and 24 weeks after starting treatment (Appendix 2 and 3A).

Clinical Pain and Treatment Tolerance will be assessed using the Visual Analog Scale for Pain (VAS) or Universal Pain Assessment Tool (Appendix 3-B).

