Function will be assessed using three validated response forms: PRTEE - An index of the severity of CET Tendinopathy¹⁸ (Appendix 2), Self-Reported Outcome Measures (SROM)¹⁶.

Level of Activity will be assessed using the activity subscale of PRTEE¹⁸ (Appendix 2). This subscale scores quantitatively the level of difficulty subjects face when they perform basic activities of daily living. It has shown to be an accurate and reliable predictor of the activity level while performing day-to-day activities.

Statistical analysis

Data will be assessed for variance homogeneity and normality. PRTEE¹⁸, and Visual Analog Scale for Pain (VAS) or Universal Pain Assessment Tool (Appendix 3-B) scores will be assessed before and after intervention. The VAS will be used for 2 different assessments: 1. Pain related to physical activity of the symptomatic arm before and after treatment. 2. Pain tolerance of the therapy treatment. Each of these assessments will be documented and evaluated separately.

Aim 2: CET Tendon thickness

Diagnostic ultrasound imaging will be performed with an FDA approved ultrasound scanner (Spark[®] System, Ardent Sound, Inc. – Mesa, AZ, see Appendix 7-B using a coupling gel (Polysonic[®], or AquaSonic[®], Parker Laboratories, Inc., Fairfield, NJ, see Appendix 7-C) by a trained sonographer or physician. Subjects will be treated seated with their arm resting on a structure that is comfortable for the subject and technologist.

CET Tendon thickness is measured before treatment(s) and at each documented assessment (Appendix 1). Paired t tests are used to compare the CET Tendon thickness means between pre- and post-treatment between the symptomatic and treated arm and the asymptomatic and untreated arm. P<0.05 is considered to be statistically significant. Any peri-CET pathology will also be documented.

Aim 3: Assessment of safety and tolerability

Subject self-assessments of treatment tolerability will be conducted immediately after treatments, and at each follow-up visit and phone survey using a 10-point visual analog scale VAS, (Appendix 3-B). The subject will be asked to report their current level of pain and the maximum level of pain experienced since the last treatment. The surveyor will remind the subject of the VAS criteria and record their reply. The VAS is the standard for assessing pain for both clinical and research purposes²².

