TITLE: STUDY TO EVALUATE THE SAFETY, EFFICACY AND TOLERANCE OF INTENSE THERAPEUTIC ULTRASOUND (ITU) FOR THE TREATMENT OF LATERAL EPICONDYLITIS

PROTOCOL NO. and WIRB NO: 20150654

DATE: March 2, 2015

Principal Investigator: [name]

The More Foundation
[name]
[name]
[name]

Sponsor: Guided Therapy Systems
[name]
[name]

Statistical Analysis Plan:

Statistical Methods

Pain Reduction:

Pain level for subjects at the region of interest was self-reported at pre-treatment, used as baseline, and again at each follow-up at 4, 8, 12, and 26 weeks following initial treatment. The pain scale subjects used to identify their level of pain was a 10-point pain scale, where 0 = no pain, 1 = slight pain, through 10 which equates to the patients' worst imaginable pain. The goal for all subjects was to reduce pain by at least 25%. For patients reporting an initial (baseline) score ranging 6-10, this reflects a VAS pain score reduction \geq a 2 point drop; for initial scores ranging 2-5, this reflects a VAS pain score reduction \geq a 1 point drop. Pain scores reported at follow-up timepoints were compared to baseline score for each subject to determine if the goal was met by dividing the difference in the follow-up and baseline pain score by the baseline pain score. The percentage of subjects that met the pain reduction goal was calculated at each timepoint for both groups by dividing the number of subjects that achieved the pain reduction goal at that timepoint by the total number of patients that gave a pain score for that timepoint.

Patient Rated Tennis Elbow Evaluation Score Reduction:

In addition to the 10-point VAS pain scale, patients self-reported answers to questions from the Patient Rated Tennis Elbow Evaluation (PRTEE) questionnaire, which has been standardized for use in research studies to evaluate patient's level of pain and function ^[10]. Scores range from 0-100, with 0 indicating no pain and 100 indicating the worst pain imaginable in a variety of daily activities. Self-reported scores were taken at baseline and each follow-up timepoint. The average score for each timepoint were calculated, and follow-up averages were compared to baseline to calculate the percentage reduction in score.

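### Aim 3 scores follow-up tolerability as unattributed elbow pain, in conflict with the Outcome measures section, and the SAP does not name the VAS item behind its pain endpoint

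*Protocol*

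**What the plan says.** **Protocol, Outcome measures.** On timing: "Treatment tolerability will be assessed immediately after each treatment using the Visual Analog Scale for Pain". The VAS is given two uses. The first is "Pain related to physical activity of the symptomatic arm before treatments and at follow-up visits and phone surveys"; the second is "2. Pain tolerance of the therapy treatment". The section adds "Each of these assessments will be documented and evaluated separately", and the Statistical analysis paragraph under Aim 1 repeats this. The visit list agrees: it names a tolerability VAS only beside the ITU session at visits 1 and 3.

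**Protocol, Aim 3.** "Subject self-assessments of treatment tolerability will be conducted immediately after treatments, and at each follow-up visit and phone survey". The question put to the subject is then spelled out: "The subject will be asked to report their current level of pain and the maximum level of pain experienced since the last treatment".

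**Protocol, Assessment of Efficacy.** The pain VAS is one of the primary endpoints, which are said to serve both efficacy and tolerability.

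**SAP, Pain Reduction.** "Pain level for subjects at the region of interest was self-reported at pre-treatment, used as baseline", and again at weeks 4, 8, 12 and 26. The goal is a fall of at least 25%. The text does not say whether the score is activity-related, current or maximum pain.

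**The concern.** The two protocol sections give the follow-up VAS different meanings. In Outcome measures it is an efficacy measure, pain when the arm is used. In Aim 3 it is a tolerability measure, but its question asks about pain in general and does not ask whether the treatment caused it. Subjects enter with more than 3 months of elbow pain, so an unattributed pain score taken weeks after a session of up to 10 minutes will mostly pick up the condition being treated. A poor efficacy result could then be reported as poor tolerability, and a good one as good tolerability.

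The pain endpoint carries a lesser risk. Aim 3 is the only place where the follow-up question is spelled out, and the SAP does not name its item. Someone collecting or analysing the data could therefore set a baseline activity score against a follow-up score that answers a different question.

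**Working it through.** The plan gives no figure on this point, and its sample-size statement is not tied to any VAS item. The check is a comparison of texts with some simple arithmetic.

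**1. Recall window in Aim 3.** Inputs: sessions at weeks 0 and 4 (Study Outline); contacts at weeks 2, 4, 8, 12 and 24 (Appendix 1); final SAP timepoint at week 26. Window = week of contact minus week of the most recent session.

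| Contact | Most recent session | Window |
|---|---|---|
| Week 2 | Week 0 | 2 − 0 = 2 weeks |
| Week 4, before the second session | Week 0 | 4 − 0 = 4 weeks |
| Week 8 | Week 4 | 8 − 4 = 4 weeks |
| Week 12 | Week 4 | 12 − 4 = 8 weeks |
| Week 24 | Week 4 | 24 − 4 = 20 weeks |
| Week 26 (SAP) | Week 4 | 26 − 4 = 22 weeks |

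**2. Behaviour of the maximum.** From week 8 onward every window starts at week 4, so each contains the one before it. The maximum over a longer window containing a shorter one is at least as large. With accurate recall, the maximum reported at week 12 cannot be below that at week 8, nor that at week 24 below that at week 12. The score can only stay level or worsen, however well the subject recovers.

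**3. Which VAS item can supply the SAP endpoint?** It needs a value before treatment and values at every follow-up, including the telephone contacts.

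| VAS item | Before treatment | Later visits | Telephone |
|---|---|---|---|
| Activity-related pain (use 1) | yes | yes | yes |
| Aim 3 current pain | none described | yes | yes |
| Aim 3 maximum pain | cannot exist before the first session | yes | yes |
| Physical-examination VAS | yes | to week 8 | no |

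Only use 1 is described at all the required times.

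**4. What a mix-up would do.** SAP ratio: (baseline − follow-up) / baseline, with response at 25% or more. Take an assumed subject with baseline activity pain 6 and, at week 8, activity pain 4, current pain 2 and maximum pain 6:
- activity: (6 − 4)/6 = 33%, responder
- current: (6 − 2)/6 = 67%, responder
- maximum: (6 − 6)/6 = 0%, non-responder

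If activity pain had not changed (6) and current pain was 4, the mixed comparison would give (6 − 4)/6 = 33%, a response with no improvement.

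**5. Direction under assumed inputs.** A simulation assumed mean baseline 6 (SD 1.5), a true fall of 20–40% by week 8 and then none, weekly noise of SD 1.0–1.5, and current pain 2 points below activity pain. Week-24 response was 44–78% for activity against activity baseline, 84–99% for current against activity baseline, and 1–16% for maximum against activity baseline. With a 30% fall and noise SD 1.0, the rate based on the maximum went from 18% to 12% to 6% at weeks 8, 12 and 24, while the activity-based rate stayed at 63%. None of these inputs comes from the documents. The runs show direction only.

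**The case against.** The strongest reply is that the protocol already separates the two VAS uses, and says so twice. Use 1 carries one description for the time before treatment and for follow-up, so its comparison is like for like. Setting baseline activity pain against follow-up current pain would break the protocol's own rule. This stands, and it is why the SAP part is secondary. The rule still does not tell the analyst which item the SAP means.

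A second reply is that Outcome measures does not say tolerability is taken only right after a session, and that asking again later can catch delayed post-procedure pain. The protocol does care about that: treatment pain lasting beyond 24 hours becomes a recordable adverse event. The purpose is sound and the fix should preserve it. The question as written does not serve it, because it never separates delayed treatment pain from elbow pain.

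Third, the SAP contains no tolerability analysis. That limits the damage to whatever is reported under Aim 3, but tolerability sits within the primary endpoint statement, so a result can be expected.

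Fourth, Appendix 3-B is a pictorial tool whose graphic was not in the text available for this review. The lack of a question stem there is not counted against the plan.

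**Conclusion.** The conflict between Outcome measures and Aim 3 is real. Followed as written, Aim 3 would report unattributed elbow pain, recalled over 4, 8 and 20 to 22 weeks from week 8 on, as treatment tolerability, with a maximum that cannot improve. That it largely reflects tendon disease is an inference from the wording and the entry criterion, but a strong one. The windows assume that the second session is given at week 4. The score taken right after each session is not affected.

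A reader might infer more: that the SAP has three interchangeable values for its responder endpoint, or that the response rate is biased upward. The documents do not support either. Activity-related pain is the only VAS described at every required time, maximum pain has no pre-treatment counterpart, and a mix-up could push the rate either way. No document gives a gap between activity and current pain. Nor would a 1-point gap at baseline 2–5, or a 2-point gap at baseline 6–10, always make a responder: 1/5 = 20%, 2/9 = 22.2% and 2/10 = 20% all miss the SAP's 25% ratio. The supportable statement is that the SAP leaves the item unnamed, with a risk that cannot be sized.

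**What to change.** - **Aim 3:** base the tolerability result on the VAS recorded immediately after ITU at visits 1 and 3, in line with Outcome measures and the visit list. Report follow-up current and maximum pain descriptively. Count delayed pain as tolerability only if the subject attributes it to the treatment.
- **SAP, Pain Reduction:** state that the responder endpoint is the activity-related VAS (use 1), asked with the same wording and recall period at week 0 and every follow-up.
- **VAS form:** label the activity-related and tolerability items separately, and add an attribution question if delayed pain is to count.

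The cost is rewording, plus one short question if attribution is wanted, with no extra visits. This assumes that the activity-related VAS is recorded as Outcome measures requires; if it was not, the SAP should say so. The downside is small: unattributed follow-up pain leaves the tolerability result but is still reported, and adverse-event recording continues unchanged.

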Subjects may discontinue from the clinical study at any time. In addition, the Principal Investigator (PI) or designee has the right to withdraw a subject for any reason that is in the best interests of the subject. The subject must inform the Investigator immediately if they intend to withdraw. Subjects may be asked to come to the study facility to complete some end of study procedures.

The Investigator can remove the subject from this study without their consent for any reason, including, but not limited to:

- His/her judgment that any condition or circumstance may jeopardize their welfare or the integrity of the study.
- Their failure to follow the instructions of the investigator(s) (protocol non-compliance)
- Subject BMI exceeds ≥ 35 during the courses of the study.
- If the study is stopped by GTS and/or Principal Investigator of the study prior to completion.

CLINICAL ASSESSMENTS

Assessment of Efficacy

Primary:

The primary endpoint(s) for efficacy and tolerability will be the total score of the PRTEE questionnaire (Appendix 2), subject self-assessment of improvement and satisfaction (SROM-Appendix 3-B), and Visual Analog Scale for Pain (VAS) or Universal Pain Assessment Tool (Appendix 3-C).

Secondary:

The secondary endpoint for efficacy will be a measured reduction in tendon thickness by diagnostic ultrasound, and a physical examination.

PRTEE Questionnaire

The PRTEE questionnaire (**Appendix 2**) evaluates three domains clinically relevant to patients (pain, function, and activity) and was specifically developed to assess the clinical severity of CET tendinopathy. It is composed of 15 questions that cover 3 domains of pain (questions 1 through 5), function for specific activities (questions 6 through 11), and general activities (questions 12 through 15). All questions are scored 0 – 10. Higher scores indicate more severe CET tendinopathy. The PRTEE questionnaire has been validated and shows good test-retest reliability¹⁸

Physical Examination

Medical History: Review patient's medical history questionnaire. Review any diagnostic imaging, tests, or work up listed under longitudinal medical record and centrality. Ask about possible trauma or history of injuries to the symptomatic arm. Review athletic history (tennis, golf, etc) and subject's pre-study exercise regimen (if any). Height, Weight (BMI) will also be documented.

History of Present Illness: Most common complaint is of elbow pain.

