
If a subject meets all the inclusion/ exclusion criteria, they will be enrolled onto the study, issued a subject number and an X-ray will be scheduled.

Visit 1 and 3: (Weeks 0 and 4) Study treatments

1. Record AEs, con meds and other events
2. Administer PRTEE-A questionnaire (Appendix 2)
3. Subject self-assessment questionnaire (Appendix 3)
4. Focused Physical Evaluation
5. Diagnostic Ultrasound images taken
6. ITU treatment, and VAS assessment of treatment tolerability.
7. Physical Therapy will be performed as described (Appendix 4 – Visit 1 only)
8. Home Cold Pack & Stretching Program review and Log (Appendix 6-A and 6-B)

Visit 2, and 4: (Weeks 2 and 8) Diagnostic Ultrasound, Self-Assessments, Physical Examination

1. Record AEs, con meds and other events;
2. Administer PRTEE-A questionnaire (Appendix 2)
3. Subject self-assessment questionnaire (Appendix 3)
4. Diagnostic Ultrasound image taken;
5. Home Cold Pack & Stretching Program review and Log (Appendix 6-A and 6-B)

Phone/Online Interviews at 3 and 6 months post treatment

1. Record AEs, con meds and other events;
2. Follow-up phone interview PRTEE-A verbally administered (Appendix 2).
3. Subject self-assessment questionnaire (Appendix 3)

STUDY TREATMENT

ITU will be performed by a trained technologist, using a clinical prototype (Ulthera FDA cleared in Sept. 2009) GEN II or GEN III designed Guided Therapy Systems, LLC. Mesa, AZ USA (Appendix 7-A).

Subjects will be treated seated with their arm resting on a structure that is comfortable for the subject and technologist. Transdermal application of ITU therapy: An average energy up to 3 joules (0.5 to 3 J) will be administered to the affected CET tendon longitudinally until the maximum number of lines (12) are reached. Each line will include individual thermal zones, less than 1 mm³ in volume, centered at a depth between 2 – 6 mm, up to 2 mm apart (figure 3).

[figure not shown]
[figure not shown]

Figure 3. Zone pitch, and depth. Tendo

Treatment pattern:

Acoustic Coupling Gel will be applied every 3-5 lines.

Figure 3-1. Zone pitch, and depth.

The study treatment will be a 10 minute session using the ultrasound therapy device with coupling gel. Subjects will be treated seated with their arm resting on a structure that is comfortable for the subject and technologist.

DIAGNOSTIC ULTRASOUND IMAGING

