Recording of adverse events will take place at all visits (see adverse event reporting form Appendix 5). Adverse events will be monitored throughout the study.

A treatment will not be administered if there is residual pain/discomfort experienced by the subject from the previous treatment.

ACCOUNTABILITY

Treatment administered to the subjects will be documented by the operator and tracked on the Case Report Form (CRF).

BREAKING THE CODE IN AN EMERGENCY

Treatment codes and allocation of treatment per subject will be accessible by the Principal Investigator of the study.

SAFETY MONITORING**ADVERSE EVENT**

An adverse event (AE) is any untoward medical occurrence in a subject, whether or not related to study product or study procedures. Adverse events include any occurrence that is new in onset, an exacerbation of a pre-existing condition and clinically significant laboratory values.

Exceptions

The following medical occurrences will not be reported as AEs;

- Pre-treatment Adverse Events; Any medical occurrence that occurs after informed consent, but before first administration of ITU treatment or first study procedure is considered as medical history and only recorded as an AE if it worsens during the study.
- Pre-existing medical condition; Events that occur with comparable frequency and severity to the subject's baseline condition are reported as medical history, not AEs unless they become exacerbated during the study.
- Pregnancy; This is not an AE however the PI must report any pregnancies to The Guided Therapy and the Institutional Review Board (IRB) for advice regarding the appropriate course of action.

Study Specific Expected Adverse Event

The following AEs are expected due to the use of these study products and/or procedures and for this specific study, they will not be regarded as AEs;

- Transient erythema may be expected as a result of the study treatment which is expected to subside after a few hours. This will not be recorded as an AE unless persistent after 24 hours.
- Subjects may experience mild-moderate tingling, warming, pain or discomfort during the study treatments. These will not be recorded as AEs unless persistent after 24 hours or if they increase to severe/unbearable sensations.

The following AEs may be expected due to the use of these study products and/or procedures and for this specific study, they will be regarded and recorded as AEs;

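### The tolerability question asked right after each ITU session has an ambiguous recall window and no item for pain during the session, so session pain is not reliably or separately measured

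*Protocol*

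**What the plan says.** Tolerance is in the study title (SAP) and in the protocol's Study Objectives.

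- **Status.** Clinical Assessments, Primary, opens: "The primary endpoint(s) for efficacy and tolerability will be the total score of the PRTEE questionnaire". The list continues with the self-reported outcome measures and the VAS or Universal Pain Assessment Tool.
- **Timing.** Outcome measures: "Treatment tolerability will be assessed immediately after each treatment using the Visual Analog Scale for Pain (VAS) or Universal Pain Assessment Tool". Assessments at Each Visit pairs the two for Visits 1 and 3: "ITU treatment, and VAS assessment of treatment tolerability".
- **Purpose.** Outcome measures, and again Statistical analysis under Aim 1, give the VAS two uses. The first is activity-related arm pain. The second is: "Pain tolerance of the therapy treatment. Each of these assessments will be documented and evaluated separately".
- **Question.** Aim 3 says: "Subject self-assessments of treatment tolerability will be conducted immediately after treatments, and at each follow-up visit and phone survey". It then gives the only wording in the documents: "The subject will be asked to report their current level of pain and the maximum level of pain experienced since the last treatment".
- **Adverse events.** Study Specific Expected Adverse Event says: "Subjects may experience mild-moderate tingling, warming, pain or discomfort during the study treatments". These count as adverse events only if they last beyond 24 hours or become severe or unbearable.
- **Analysis.** The SAP has no tolerability analysis. Its pain analysis uses pain at the region of interest at baseline and at 4, 8, 12 and 26 weeks.

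**The concern.** The protocol promises a distinct measurement of how well the therapy is tolerated, but the question it supplies is not tied to the therapy session. One sentence serves both the reading taken just after a session and every later visit and call. It makes sense at follow-up. Just after a session, it does not say which period the subject should rate.

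The subjects already have elbow pain, since entry requires pain lasting more than 3 months, so a loosely framed pain rating will pick up the disease as well as the procedure. If some subjects include the session in their answer and others do not, the scores cannot be compared between subjects or between session 1 and session 2. A session that hurt moderately while running and settled at once could be scored as well tolerated. Conversely, a high score after session 2 could be ordinary tendon pain from the preceding month. Session pain that is not asked about at the time cannot be reliably recovered later.

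**Working it through.** The plan gives no figure to reproduce, so the check sets the question against its timing and purpose.

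**Inputs (all Protocol).** Sessions at weeks 0 and 4, each up to 10 minutes (Study Outline). Up to 25 subjects (Selection of Subjects). Tolerability rated immediately after each session (Outcome measures; Aim 3). Two items, current pain and maximum pain since the *last treatment* (Aim 3).

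**Step 1: current pain.** This is answered after energy delivery has stopped. It captures residual treatment pain together with any resting elbow pain. It does not capture pain felt only while the device was on.

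**Step 2: maximum pain.** The result depends on what *last treatment* means, which the protocol does not define.

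| Meaning | After session 1 (Visit 1, week 0) | After session 2 (Visit 3, week 4) |
|---|---|---|
| Session just finished, taken literally | Window opens once exposure has ended | Same |
| Previous session | No previous session exists | Window of 4 − 0 = about 4 weeks; session 2 mixed with a month of elbow pain |
| Session just finished, with *since* taken to include it | Session pain included | Session pain included |

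Only the third, looser meaning gives the intended quantity, and nothing in the text directs the subject or the surveyor to it.

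**Step 3: is session pain recorded elsewhere?** The adverse event rule excludes expected mild to moderate sensations that settle within 24 hours, and records severe or unbearable ones. No VAS score is tied to that threshold; the severity definitions rest on interference with daily activity. The satisfaction item (SROM 6, Appendix 3-A) asks about the treatment received but is not a pain score. The expected range of session pain therefore depends on the VAS item.

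**Step 4: extent.** The wording applies to at most 25 × 2 = 50 post-session ratings. This counts the ratings exposed to the ambiguity, not those in error. Under the literal first meaning, session pain can be missed. Under the second, the session 2 maximum may exceed the session's own pain. The documents contain no scores from which to estimate either effect.

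**The case against.** The best defence is that the protocol's intent is clear. It names pain tolerance of the therapy as a separate VAS use and schedules it with the session, so a sensible assessor would ask about the session. The Aim 3 sentence, followed as it is by an instruction to a surveyor, reads most naturally as a script for follow-up visits and calls. A subject asked straight after treatment may well include the session. Severe or unbearable session pain is recorded as an adverse event regardless of duration.

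Much of this stands. A reader might infer that the measure misses treatment pain altogether, that all 50 ratings are too low, or that a very painful session would leave no trace. The documents support none of these:

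- residual pain is captured by the current-pain item;
- some subjects may include the session;
- on one meaning, the session 2 window contains session 2 and could overstate its pain;
- pain that reaches severe or unbearable is recorded as an adverse event.

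Any figure for the number of points lost would rest on invented scores.

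The defence does not close the gap. Stated intent is not a question, and Aim 3 expressly applies its wording to the reading immediately after treatments. If that sentence is instead only a follow-up script, the immediate reading has no wording at all. Leaving the recall period to each subject or assessor is itself what makes the ratings non-comparable.

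**Conclusion.** The point holds in a limited form. The protocol undertakes to measure pain tolerance of the treatment as part of a primary measure. Its only wording leaves the recall window ambiguous at the moment of measurement and has no item for pain during the session. Session pain is therefore not reliably or separately measured. The exposed part is the expected mild to moderate pain that settles within 24 hours, because the adverse event rule does not record it either. Up to 50 ratings use the wording, but the size and direction of the error cannot be stated.

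This rests on two assumptions: that the Aim 3 wording is used as written just after each session, and that the scale in Appendix 3-B carries no recall period of its own. Only the introductory text of that tool could be read, and it gives none. If the form does state one, the protocol text should be aligned with it. The point concerns only the immediate post-session reading, not the pain ratings at follow-up. It should be corrected because the measure is primary and the correction is small.

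**What to change.** In Aim 3, for the reading immediately after each session, ask: *Rate the worst pain you felt during the treatment you have just had (0–10).* Record it separately for session 1 and session 2, and use it as the VAS for pain tolerance of the therapy. Keep current elbow pain as a separate item. Use the *since the last treatment* item only at follow-up visits and calls, stating which session it refers to at each. At a minimum, state the recall period of the immediate rating.

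The cost is one reworded item on an existing form. The downside is that tolerability scores may look less favourable. No treatment, schedule or clinical rule changes.
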